9.1.5.6 Quality of Life and Productivity data Analyses

Primary study population for all quality of life and productivity data analyses will be based on ITT population. The HADS, DLQI, EQ5D and productivity data will be summarized by treatment group and analysis visit. Details of the analyses will be provided in the SAP.

9.2 Sample size assumption

Sample size is estimated using MCP-Mod (Bretz 2005) approach by selecting a set of candidate dose response shapes based on EASI response in previous Phase 2a study (CIM003JG study report 2017). The following models are considered as candidates in the estimation of sample size.

Linear	Emax	Sigmoid Emax
Linear	1. ED50 =10mg 2. ED50=30mg	1. ED50=10mg, H (Hill)=1 2. ED50=10mg, H (Hill)=2 3. ED50=10mg, H (Hill)=3 4. ED50=15mg, H (Hill)=2 5. ED50=20mg, H (Hill)=4 6. ED50=30mg, H (Hill)=2
ED50=dose produces 50% of maximum effect		

Assuming a placebo response of 35%, standard deviation 45% and a maximum treatment difference of 30%, in terms of percent change in EASI, 50 subjects per arm will provide at least

90% power to detect a statistically significant dose-response for at least one model at 1-sided significance level of 0.025.

10 TRAINING / MONITORING / DATA MANAGEMENT / QUALITY ASSURANCE

10.1 Personnel training

CRA and all relevant personnel will be trained prior to study initiation on the condition to be treated, the Standard Operating Procedures (SOPs) to be used in this clinical trial, the protocol, and all study-specific procedures. Team organization, communication, and operational issues will also be discussed and agreed upon.

Investigators, evaluators, study coordinators, pharmacists and other applicable personnel are recommended to attend an investigator meeting. During the meeting, participants will be trained on the protocol, ICH-GCP, study-specific procedures (including efficacy assessment scales and instruction for use of the study drug), IRT and eCRF completion.

All personnel involved in the study conduct will receive training prior to participating in any procedure and/or evaluation. Each study center will have a training record as part of the site file and Trial Master File.

10.2 Clinical monitoring

The conduct of the clinical trial will be closely monitored by Sponsor representatives to verify adherence to the clinical trial protocol, ICH-GCP guidelines, and applicable SOPs. All monitoring procedures will be detailed in the monitoring plan.

The investigator will allow the CRO/Sponsor representatives, to have direct access to all clinical trial records, eCRF, corresponding subject medical records, study drug dispensing records, and any other documents considered source documentation. Additionally, the CRO/Sponsor representative is to have access to the study drug storage area and clinical trial facilities. The investigator also agrees to assist the representative if required.

A partially unblinded CRA will be designated for each investigational site, and is responsible only for monitoring the records related to study drug in the pharmacy study file. The partially unblinded CRA will have no access to other data collected during the study (including the source data at the investigational site and the eCRF), and will also be instructed to not discuss trial-related matters with the investigator/evaluator, the subjects or the blinded CRA.

10.3 Data management

All data management procedures will be detailed in a data management plan (DMP).

The DMP will describe the clinical data management system that will be used to collect data, and who is responsible for performing the data management activities. Computerized edit checks and review processes will be performed on an ongoing basis as outlined in the DMP until all data clarifications are resolved. The data will be exported to be stored in SAS datasets. After all data clarifications are resolved, coding is approved, SAE/pregnancy reconciliation has been completed and subject's evaluability is determined, the database will be locked.

Pruritus NRS, PCS, sleep disturbance NRS, DPS, DLQI, HADS and EQ5D will be collected using an electronic device.

10.4 Quality assurance / audit / inspection

The clinical trial is conducted under the sponsorship of Galderma in compliance with the applicable international and local regulatory requirements as well as applicable ICH guidelines and in accordance with the SOPs for clinical trial conduct and monitoring from sponsor and/or CRO.

Audits of clinical trial centers may be conducted by the Sponsor/CRO representatives, and inspection may be performed by regulatory authority inspectorates or IRBs/IECs before, during, or after the clinical trial. The investigator will allow and assist the Sponsor/CRO representatives, IRBs/IECs and any regulatory agency to have direct access to all requested clinical trial-related records. For the audits performed by, or on behalf of, sponsor auditors, audit certificate will be provided by quality assurance.

10.5 Changes in clinical trial conduct / amendments

10.5.1 Clinical trial conduct

With the exception of avoiding an immediate risk to a subject, the investigator should not deviate from the clinical trial protocol or implement any changes without written approval from the Sponsor and prior review and documented approval/favorable opinion from the IRB/IEC of a protocol amendment.

Changes that involve only logistical or administrative changes to the clinical trial protocol are authorized. The investigator should document and explain any deviation from the clinical trial protocol.

10.5.2 Amendments

The Sponsor may modify the clinical trial protocol at any time for ethical, medical, or scientific reasons. Any amendments will be handled according to applicable local regulations.

The Sponsor does not have to notify non-substantial amendments to the competent authorities or IRB/IEC. However, non-substantial amendments will be recorded and detailed in subsequent submissions (e.g., in the subsequent notification of a substantial amendment).

11 ETHICS AND GENERAL CLINICAL TRIAL CONDUCT CONSIDERATIONS

11.1 Independent Ethics Committee (IEC) or Institutional Review Board (IRB)

This clinical trial protocol and all amendments will be reviewed and approved by the appropriate IECs/IRBs.

11.2 Ethical conduct of the clinical trial

This clinical trial will be conducted in accordance with the protocol, the HELSINKI declaration (1964) and subsequent amendments, and the ICH GCP, and in compliance with applicable regulatory requirements.

11.3 Subject information and consent

All subjects who participate in this clinical trial are required to be fully informed about the clinical trial in accordance with GCPs guidelines, federal regulations, HIPAA (for the U.S), PIPEDA (for Canada), and guidelines and in accordance with local requirements.

The ICF approved by an IRB/IEC will be fully explained to the subject. Prior to enrolment into the clinical trial, the subject will sign and date the consent form. The investigator is responsible for maintaining each subject's consent form in the site file and providing each subject with a copy of the signed and dated consent form.

11.4 Contractual requirements

A contractual agreement will be signed between the CRO/Sponsor and each investigator/institution. This document will contain supplementary information, including financial terms, confidentiality, the clinical trial schedule, third party responsibility, and publication rights.

11.5 Data collection and archiving

11.5.1 Data collection

The investigator must maintain all required records for all subjects. Data for this clinical trial will be recorded in the subject's source documents (including electronic device) and in the eCRF provided by the Sponsor/CRO. All data should be recorded in the eCRF completely and promptly.

11.5.2 Source documentation

The investigator must keep accurate separate records (except those defined below for which eCRF could be considered as source documentation) of all subject visits, and ensure that they include all pertinent clinical trial-related information. A statement should be made indicating that the subjects have been included in this clinical trial and have provided signed written ICF. All AEs must be thoroughly documented.

Specifically, source documentation supporting the subjects' inadequate response to topical treatment (inclusion criterion #7, see Section 5.2.1) include medical records (including pharmacy records) and documented conversation between the investigator and other healthcare provided. Information based on subject's medical interview with no other supporting evidence cannot be accepted.

Results of any laboratory tests conducted during the clinical trial should also be included in the source documentation. Scores of EASI and SCORAD will be calculated automatically in the eCRF and will therefore be considered as e-source data; however, the components of EASI and SCORAD must be documented on a separate source document. Data documented on the electronic device directly (e.g. pruritus NRS) will also be considered as e-source data.

11.5.3 Archives

All pertinent data, samples, photographs, correspondence, and reports, the original or amended clinical trial protocol, and all other material relating to the clinical trial will be maintained securely in sponsor/CRO/investigator/institution archives as specified in section 8 of ICH-GCP, and according to the applicable regulatory requirements, for the legally required duration for archiving. The investigator/institution should take measures to prevent accidental or premature destruction of these documents.

If the principal investigator retires, relocates, or withdraws from the responsibility of keeping the clinical trial records for any other reasons, custody must be transferred to a person who will accept the responsibility. The Sponsor/CRO must be notified in writing of the name and address of the new custodian.

11.6 Insurance

A certificate attesting third party coverage of CRO/sponsor will be provided upon request.

11.7 Investigator and Administrative Structure

Designation of [REDACTED] CCI as Coordinating Investigator (CI) was done pursuant to the European Agency for the Evaluation of Medicinal Products (EMA) guidance on “Coordinating Investigator Signature of Clinical Trial Reports”.

13 APPENDICES

APPENDIX 1 AAD CONSENSUS CRITERIA FOR AD DIAGNOSIS

Features to be considered in diagnosis of patients with atopic dermatitis:

- **ESSENTIAL FEATURES;** must be present:
 - Pruritus
 - Eczema (acute, subacute, chronic):
 - Typical morphology and age-specific patterns*
 - Chronic or relapsing history

**Patterns include:*

 - 1) *facial, neck, and extensor involvement in infants and children;*
 - 2) *Current or prior flexural lesions in any age group;*
 - 3) *Sparing of groin and axillary regions.*
- **IMPORTANT FEATURES;** seen in most cases, adding support to the diagnosis:
 - Early age of onset
 - Atopy
 - Personal and/or family history
 - IgE reactivity
 - Xerosis
- **ASSOCIATED FEATURES;** these clinical associations help to suggest the diagnosis of AD but are too non-specific to be used for defining or detecting AD for research and epidemiologic studies:
 - Atypical vascular responses (e.g., facial pallor, white dermographism, delayed blanch response)
 - Keratosis pilaris / pityriasis alba / hyperlinear palms / ichthyosis
 - Ocular / periorbital changes
 - Other regional findings (e.g., perioral changes / periauricular lesions)
 - Perifollicular accentuation / lichenification / prurigo lesions
- **EXCLUSIONARY CONDITIONS;** it should be noted that a diagnosis of AD depends on excluding conditions such as:
 - Scabies
 - Seborrheic dermatitis
 - Contact dermatitis (irritant or allergic)
 - Ichthyoses
 - Cutaneous T-cell lymphoma
 - Psoriasis
 - Photosensitivity dermatoses
 - Immune deficiency diseases
 - Erythroderma of other causes

APPENDIX 2 Eczema Area and Severity Index (EASI)

Body region	EASI score
Head/Neck (H)	$(E + I + Ex + L) \times Area \times 0.1$
Upper limbs (UL)	$(E + I + Ex + L) \times Area \times 0.2$
Trunk (T)	$(E + I + Ex + L) \times Area \times 0.3$
Lower limbs (LL)	$(E + I + Ex + L) \times Area \times 0.4$
EASI =	Sum of the above 4 body region scores

The degree of severity of each sign (E=erythema, I=induration/papulation, Ex=excoriation, L=lichenification) in each of the 4 body regions is evaluated based on a scale ranging from 0 to 3 (0: none; 1: mild; 2: moderate; 3: severe), with half points allowed.

Area (the affected body area) is defined as follows: 0= 0%; 1=1-9%; 2=10-29%; 3=30-49%; 4=50-69%; 5=70-89%; 6=90-100%. Among the four zones, trunk includes the genital area, and lower limbs include the buttocks ([Hanifin 2001](#)).

APPENDIX 3 Investigator's Global Assessment (IGA)

Status	Score	Definition
Clear	0	Minor, residual hypopigmentation/hyperpigmentation, no erythema or induration/papulation, no oozing/crusting.
Almost clear	1	Trace faint pink erythema, with barely perceptible induration/papulation and no oozing/crusting.
Mild	2	Faint pink erythema with mild induration/papulation and no oozing/crusting.
Moderate	3	Pink-red erythema with moderate induration/papulation with or without oozing/crusting.
Severe	4	Deep or bright red erythema with severe induration/papulation with oozing/crusting.

APPENDIX 4 SCORing Atopic Dermatitis (SCORAD)

Figures in parenthesis for children under two years

A: EXTENT Please indicate the area involved

B: INTENSITY

CRITERIA	INTENSITY
Erythema	
Edema/Papulation	
Oozing/crust	
Excoriation	
Lichenification	
Dryness *	

MEANS OF CALCULATION
 INTENSITY ITEMS
 (average representative area)
 0= absence
 1= mild
 2= moderate
 3= severe
 * Dryness is evaluated on uninvolved areas

C: SUBJECTIVE SYMPTOMS PRURITUS+SLEEP LOSS

SCORAD $A/5+7B/2+C$

Visual analog scale (average for the last 3 days or nights)
PRURITUS (0to10) **SLEEP LOSS** (0to10)

Extent: The extent of body area affected by atopic dermatitis

Intensity: To determine the intensity, select a representative area and assess the intensity of each as 0 (absence), 1 (mild), 2 (moderate), or 3 (severe). Dryness should be assessed in an area without inflammation or application of moisturizer within 8 hours prior to the assessment.

Subject symptoms: Subject evaluation of pruritus (itch) and sleep loss during the last 3 days prior to the visit

APPENDIX 5 Pruritus Numeric Rating Scale (NRS)

For average itch intensity: “On a scale of 0 to 10, with 0 being ‘no itch’ and 10 being ‘worst itch imaginable’, how would you rate your itch overall during the previous 24 hours?”

0	1	2	3	4	5	6	7	8	9	10
---	---	---	---	---	---	---	---	---	---	----

No itch worst itch imaginable

For maximum itch intensity: “On a scale of 0 to 10, with 0 being ‘no itch’ and 10 being ‘worst itch imaginable’, how would you rate your itch at the worst moment during the previous 24 hours?”

0	1	2	3	4	5	6	7	8	9	10
---	---	---	---	---	---	---	---	---	---	----

[figure not shown]
No itch worst itch imaginable

APPENDIX 6 Pruritus Categorical Scale (PCS)

Please rate your overall itch during the previous 24 hours

Score	Definition
0	absence of pruritus
1	mild pruritus (occasional slight itching/scratching)
2	moderate pruritus (constant or intermittent itching/scratching that does not disturb sleep)
3	severe pruritus (bothersome itching/scratching that disturbs sleep).

APPENDIX 7 Dynamic Pruritus Scale (DPS)

APPENDIX 8 5-D ITCH SCALE

1. **Duration:** During the last 2 weeks, how many hours a day have you been itching?

Less than 6hrs/day	6-12 hrs/day	12-18 hrs/day	18-23 hrs/day	All day
				
1	2	3	4	5

2. **Degree:** Please rate the intensity of your itching over the past 2 weeks

Not present	Mild	Moderate	Severe	Unbearable
				
1	2	3	4	5

3. **Direction:** Over the past 2 weeks has your itching gotten better or worse compared to the previous month?

Completely resolved	Much better, but still present	Little bit better, but still present	Unchanged	Getting worse
				
1	2	3	4	5

4. **Disability:** Rate the impact of your itching on the following activities over the last 2 weeks

	Never affects sleep	Occasionally delays falling asleep	Frequently delays falling asleep	Delays falling asleep and occasionally wakes me up at night	Delays falling asleep and frequently wakes me up at night	
Sleep						
	1	2	3	4	5	
	N/A	Never affects this activity	Rarely affects this activity	Occasionally affects this activity	Frequently affects this activity	Always affects this activity
Leisure/Social						
		1	2	3	4	5
Housework/Errands						
		1	2	3	4	5
Work/School						
		1	2	3	4	5

5. **Distribution:** Mark whether itching has been present in the following parts of your body over the last 2 weeks. If a body part is not listed, choose the one that is closest anatomically.

	Present		Present
Head/Scalp		Soles	
Face		Palms	
Chest		Tops of Hands/Fingers	
Abdomen		Forearms	
Back		Upper Arms	
Buttocks		Points of Contact w/ Clothing (e.g waistband, undergarment)	
Thighs		Groin	
Lower legs			
Tops of Feet/Toes			

APPENDIX 9 Sleep disturbance Numeric Rating Scale (NRS)

On a scale of 0 to 10, with 0 being ‘no sleep loss related to signs/symptoms of AD’ and 10 being ‘I cannot sleep at all due to the signs/symptoms of AD’, how would you rate your sleep last night?”

0	1	2	3	4	5	6	7	8	9	10
---	---	---	---	---	---	---	---	---	---	----

No sleep loss I cannot sleep at all

APPENDIX 10 Dermatology Life Quality Index (DLQI)

The aim of this questionnaire is to measure how much your skin problem has affected your life **OVER THE LAST WEEK**. Please tick (✓) one box for each question.

- | | | |
|---|-------------------------------------|---------------------------------------|
| 1. Over the last week, how itchy, sore, painful or stinging has your skin been? | Very much  | |
| | A lot  | |
| | A little  | |
| | Not at all  | |
| 2. Over the last week, how embarrassed or self conscious have you been because of your skin? | Very much  | |
| | A lot  | |
| | A little  | |
| | Not at all  | |
| 3. Over the last week, how much has your skin interfered with you going shopping or looking after your home or garden ? | Very much  | |
| | A lot  | |
| | A little  | |
| | Not at all  | Not relevant  |
| 4. Over the last week, how much has your skin influenced the clothes you wear? | Very much  | |
| | A lot  | |
| | A little  | |
| | Not at all  | Not relevant  |
| 5. Over the last week, how much has your skin affected any social or leisure activities? | Very much  | |
| | A lot  | |
| | A little  | |
| | Not at all  | Not relevant  |
| 6. Over the last week, how much has your skin made it difficult for you to do any sport ? | Very much  | |
| | A lot  | |
| | A little  | |
| | Not at all  | Not relevant  |
| 7. Over the last week, has your skin prevented you from working or studying ? | Yes  | |
| | No  | Not relevant  |
| If "No", over the last week how much has your skin been a problem at work or studying ? | A lot  | |
| | A little  | |
| | Not at all  | |
| 8. Over the last week, how much has your skin created problems with your partner or any of your close friends or relatives ? | Very much  | |
| | A lot  | |
| | A little  | |
| | Not at all  | Not relevant  |
| 9. Over the last week, how much has your skin caused any sexual difficulties ? | Very much  | |
| | A lot  | |
| | A little  | |
| | Not at all  | Not relevant  |
| 10. Over the last week, how much of a problem has the treatment for your skin been, for example by making your home messy, or by taking up time? | Very much  | |
| | A lot  | |
| | A little  | |
| | Not at all  | Not relevant  |

Please check you have answered **EVERY** question. Thank you.

APPENDIX 11 Hospital Anxiety and Depression Scale (HADS)

Instructions: Doctors are aware that emotions play an important part in most illnesses. If your doctor knows about these feelings he or she will be able to help you more. This questionnaire is designed to help your doctor know how you feel. Read each item and circle the reply which comes closest to how you have been feeling in the past week. Don't take too long over your replies: your immediate reaction to each item will probably be more accurate than a long thought out response.

I feel tense or 'wound up':	A	I feel as if I am slowed down:	D
Most of the time	3	Nearly all of the time	3
A lot of the time	2	Very often	2
Time to time, occasionally	1	Sometimes	1
Not at all	0	Not at all	0
I still enjoy the things I used to enjoy:	D	I get a sort of frightened feeling like 'butterflies in the stomach':	A
Definitely as much	0	Not at all	0
Not quite so much	1	Occasionally	1
Only a little	2	Quite often	2
Not at all	3	Very often	3
I get a sort of frightened feeling like something awful is about to happen:	A	I have lost interest in my appearance:	D
Very definitely and quite badly	3	Definitely	3
Yes, but not too badly	2	I don't take as much care as I should	2
A little, but it doesn't worry me	1	I may not take quite as much care	1
Not at all	0	I take just as much care as ever	0
I can laugh and see the funny side of things:	D	I feel restless as if I have to be on the move:	A
As much as I always could	0	Very much indeed	3
Not quite so much now	1	Quite a lot	2
Definitely not so much now	2	Not very much	1
Not at all	3	Not at all	0
Worrying thoughts go through my mind:	A	I look forward with enjoyment to things:	D
A great deal of the time	3	A much as I ever did	0
A lot of the time	2	Rather less than I used to	1
From time to time but not too often	1	Definitely less than I used to	3
Only occasionally	0	Hardly at all	2
I feel cheerful:	D	I get sudden feelings of panic:	A
Not at all	3	Very often indeed	3
Not often	2	Quite often	2
Sometimes	1	Not very often	1
Most of the time	0	Not at all	0
I can sit at ease and feel relaxed:	A	I can enjoy a good book or radio or TV programme:	D
Definitely	0	Often	0
Usually	1	Sometimes	1
Not often	2	Not often	2
Not at all	3	Very seldom	3

Questions relating to anxiety are indicated by an 'A' while those relating to depression are shown by a 'D'. Scores of 0-7 in respective subscales are considered normal, with 8-10 borderline and 11 or over indicating clinical 'caseness'

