3.2.6.2 Hospital Anxiety and Depression Scale (HADS)

HADS is a validated questionnaire containing 14 items, 7 each for anxiety and depression. Subject will rate each question ranging from 0 to 3, and the total score ranges from 0 to 21 for each sub-scale. HADS will be administered only to the subset of subjects who fluently speak a language in which the questionnaire is presented.

For each sub-scale, the score will be categorized as follows:

- 0-7 = Normal
- 8-10 = Borderline abnormal (borderline case)
- 11-21 = Abnormal (case):

HADS will be assessed at baseline, weeks 12, 24, or early termination visit when applicable.

At a given visit, there must be responses to at least 6 out of 7 questions within each sub-scale of anxiety and depression. If fewer than 6 responses, then the sub-scale will be set to missing.

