4.9.3 Quality of Life and Productivity data Analyses

Primary study population for all QoL and productivity data analyses will be based on ITT population. The DLQI, HADS, EQ5D and productivity data will be summarized by treatment group and visit.

By-subject listings of these data should be provided.

4.9.3.1 Change from baseline in DLQI at each visit up to week 24

This endpoint will be analyzed as the primary efficacy endpoint using a MMRM approach.

In addition, the following analyses will be performed:

- A shift table (by visit) will be generated using the categories as described in Section 3.2.6.1.
- Change from baseline in each sub-scale (see Section 3.2.6.1) at each visit up to week 24 will be analyzed as the primary efficacy endpoint using a MMRM approach.

- Proportion of subjects achieving a change in DLQI score of at least 4 points at each visit up to week 24 will be analyzed using a CMH test as described in Section 4.7.3.1.

4.9.3.2 Change from baseline in HADS at each visit up to week 24

The following endpoints will be analyzed as the primary efficacy endpoint using a MMRM approach.

- Change from baseline in HADS anxiety sub-score at each visit up to week 24
- Change from baseline in HADS depression sub-score at each visit up to week 24

In addition, the following analyses will be performed using a CMH test as described in Section 4.7.3.1:

- Proportion of subjects with HADS anxiety sub-score ≥ 11 at each visit up to week 24
- Proportion of subjects with HADS depression sub-score ≥ 11 at each visit up to week 24

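### The only HADS item key in the documents transposes the two worst scores of one depression item (0, 1, 3, 2); any sub-score computed from it would be off by a point for those answers

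*Protocol*

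**What the plan says.** Protocol section 7.5.2 describes the HADS and points to Appendix 11 for the instrument. The appendix prints the questionnaire with a score beside each answer, marks each item as anxiety (A) or depression (D), and gives the sub-scale bands: 0 to 7 normal, 8 to 10 borderline, 11 or more a case.

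For the depression item "I look forward with enjoyment to things" the printed scores are:

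- "A much as I ever did": 0
- "Rather less than I used to": 1
- "Definitely less than I used to": 3
- the fourth answer (hardly at all): 2

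SAP section 3.2.6.2 gives the structure and range of the scale: "HADS is a validated questionnaire containing 14 items, 7 each for anxiety and depression", and "Subject will rate each question ranging from 0 to 3, and the total score ranges from 0 to 21 for each sub-scale". It repeats the bands and requires at least 6 of 7 answers per sub-scale. It lists no item scores and does not refer to Appendix 11.

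SAP section 4.9.3.2 plans two inferential analyses of the depression sub-score. One is an MMRM on "Change from baseline in HADS depression sub-score at each visit up to week 24". The other is a CMH test on the proportion with a sub-score of 11 or more. Protocol section 10.3 states that the HADS is collected on an electronic device.

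**The concern.** The four answers run from undiminished enjoyment to almost none, so the scores should rise with them. As printed, the most impaired answer scores less than the one before it. A subject who worsens from the third to the fourth answer would be scored as improving.

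The SAP writes out the scoring of the DLQI (SAP Appendix 3) and the EQ5D (SAP Appendix 4) but not of the HADS. A programmer working only from these two documents would therefore find no item key except the one in Protocol Appendix 11. At stake is the depression sub-score in the MMRM and in the case analysis, if either is derived from that key.

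**Working it through.** **Inputs.** The item scores and bands come from Protocol Appendix 11. The range and number of items come from Protocol section 7.5.2 and SAP section 3.2.6.2. The cut-off of 11 comes from SAP section 4.9.3.2.

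**Step 1: the stated range.** Seven items scored 0 to 3 give a maximum of 7 × 3 = 21 and a minimum of 0, as stated. The printed key also reaches 21, so the range by itself does not reveal the problem.

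**Step 2: order of scores in every item, in printed order.**

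| Sub-scale | Item | Scores |
|---|---|---|
| Depression | slowed down | 3, 2, 1, 0 |
| Depression | still enjoying things | 0, 1, 2, 3 |
| Depression | appearance | 3, 2, 1, 0 |
| Depression | laughing | 0, 1, 2, 3 |
| Depression | looking forward | **0, 1, 3, 2** |
| Depression | cheerful | 3, 2, 1, 0 |
| Depression | book, radio or TV | 0, 1, 2, 3 |
| Anxiety | tense | 3, 2, 1, 0 |
| Anxiety | butterflies | 0, 1, 2, 3 |
| Anxiety | something awful | 3, 2, 1, 0 |
| Anxiety | restless | 3, 2, 1, 0 |
| Anxiety | worrying thoughts | 3, 2, 1, 0 |
| Anxiety | panic | 3, 2, 1, 0 |
| Anxiety | at ease | 0, 1, 2, 3 |

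Thirteen of 14 are monotone. Only the looking-forward item is not.

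**Step 3: all-worst answers on the depression sub-scale.** With the printed key: 6 × 3 + 2 = 20. With the item in order: 6 × 3 + 3 = 21. Under the printed key, 21 is reached only by giving the second-worst answer to this item.

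**Step 4: error at one visit (printed minus ordered).** Third answer: 3 − 2 = +1. Fourth answer: 2 − 3 = −1. First and second answers: 0. Across a group, the mean sub-score shifts by p3 − p4, where p3 and p4 are the proportions giving the third and fourth answers. The documents give neither proportion.

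**Step 5: error in change from baseline.**

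| Move on this item | Printed change | Ordered change | Error |
|---|---|---|---|
| third to fourth (worse) | 2 − 3 = −1 | 3 − 2 = +1 | −2 |
| fourth to third (better) | 3 − 2 = +1 | 2 − 3 = −1 | +2 |
| second to third | 3 − 1 = +2 | 2 − 1 = +1 | +1 |
| second to fourth | 2 − 1 = +1 | 3 − 1 = +2 | −1 |

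Moves between the first answer and the third or fourth carry the same 1-point errors as those from the second. The sign is wrong only for moves between the third and fourth answers.

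**Step 6: case status at 11 or more, all seven items answered.** Let s be the total of the other six items. Status differs between the two keys only at s = 8:

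- third answer: printed 8 + 3 = 11 (case), ordered 8 + 2 = 10 (not a case);
- fourth answer: printed 8 + 2 = 10 (not a case), ordered 8 + 3 = 11 (case).

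**The case against.** The strongest reply is that Appendix 11 may be only a specimen of the form. No section says that sub-scores are computed from it. The HADS is completed on an electronic device whose scoring program is not shown, and the SAP's HADS sections never cite the appendix. The same item has another slip in its first answer, "A much as I ever did", which suggests careless retyping and not a deliberate scoring rule. The text here was also read from a PDF by a program, so a reading fault is possible.

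Much of this stands. A reader might infer that the MMRM and case results are wrong, or that stored scores must be recalculated. The documents do not support either inference, because they do not show which key the device or the analysis program uses. A reader might also infer that the 0 to 21 range is contradicted. It is not, since 21 remains attainable.

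What does not stand is that the page can be left alone. Protocol section 7.5.2 sends the reader to it, it carries item scores and cut-offs, and nothing in either document overrides it. A reading fault is unlikely: the anxiety item printed beside this one keeps its scores in order on the same two lines, as does every other item.

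It may also be said that one form is used in all arms, so the error would not favour any of them. That is broadly fair, though not guaranteed. By step 4, the comparison is undisturbed only if p3 − p4 changes equally from baseline in each arm.

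**Conclusion.** The key is wrong as printed: one of 14 items is out of order, and it is the only HADS item key in the documents. That conclusion rests on the wording of the answers and the pattern of the other 13 items, and needs no outside copy of the questionnaire.

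The effect on the data is conditional. If the printed key was programmed, the error is 1 point of 21 at a visit for a subject giving the third or fourth answer. It reaches 2 points in change from baseline, with the wrong sign, for a move between those two answers. Case status flips only where the correct total is 10 with the third answer or 11 with the fourth; a total of 10 or 11 alone is not enough.

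The reach is narrow. The HADS is a quality-of-life measure, planned at baseline, weeks 12 and 24 or early termination, in subjects for whom a suitable language version exists. The primary endpoint, the sample size and the anxiety sub-score are not affected. This is a minor correction with a verification step attached.

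**What to change.** 1. Look at the source page of Protocol Appendix 11 to rule out a reading fault.
2. If the page reads as above, correct the item to 0, 1, 2, 3.
3. State the 14 HADS item scores in the SAP, as is already done for the DLQI and EQ5D, so that the derivation does not depend on a protocol appendix.
4. Before database lock, verify the device's scoring and the analysis program against the corrected key.
5. Re-derive depression sub-scores only if that check shows that the wrong key was used.

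The cost is one line in the appendix, a short table in the SAP and one programming check. No design, sample-size or data-collection change is needed.
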